## **Feasibility and Sample Size**

**Part A:** Based on previous studies, there are about 200 in-patients per year receiving PN. All patients will be assessed as per standard medical guidelines for PN and it is expected that 90% will agree to participate in the project. We calculate that we will have enrolled about 50 patients for Part A, before we start with part B. We will later include 150 more patients from Part B to have a total of 200 patients. We will compare the data obtained with 100 retrospective patients to see if the actions of the nutrition team changed since we started the project.

**Part B:** When we receive the ClinOleic in the hospital, patients will receive either SO-based lipid emulsion (Intralipid= 150 patients) or OO-based lipid emulsion (ClinOleic=150 patients) on an alternate basis (one-to-one) for the duration of the PN.

The total number of patients including part A and part B is estimated to be 350 patients. It is expected to take about one and a half years to recruit this number of patients.

For the Intralipid and ClinOleic analysis, we based our sample size on a study that evaluated the use of either SO or SO + fish oil (FO) in 206 patients with gastrointestinal or colonic cancer during 7 days after surgery and found that the patients that were given the FO treatment had significantly shorter length of stay than the SO group (Mean (SD) 15(5) versus 17(8) p= 0.041). Also, they had fewer infectious complications (50). Another study compared soybean oil and soybean oil+FO in 57 elderly patients with colorectal cancer. In the treatment group, there were fewer infectious complications and incidences of systemic inflammatory response syndrome (SIRS), and shorter lengths of hospital stay were observed(51).

Based on this, we estimate that a sample size of 150 in each group with a power of 0.8 and alpha of 0.05 will be sufficient to show a similar difference in length of stay between the two groups (soybean or ClinOleic) using the online sample size calculation provided by G.W. Snedecor & W.G. Cochran  
<http://www.biomath.info/power/ttest.htm>.

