## **Statistical analysis**

**Part A:** Descriptive statistics will be performed. Results will be expressed as absolute numbers and percentages, mean  $\pm$  standard deviation (SD) or median (minimum; maximum) depending on the variable types and distributions, separately for the prospective and the retrospective dataset.

For the prospective study, multivariate logistic regression will be performed to identify risk factors associated with specific PN prescription: for example, inadequate administration of PN. In addition, data from the prospective study and the retrospective chart review will be compared by unpaired t-test, Mann-Whitney-test or chi-square test as appropriate. A p value  $<0.05$  will be considered statistically significant. **Part**

**B:** For the Intralipid and the ClinOleic analysis, all variables will be tested for normal distribution (Shapiro Wilks test). *Primary outcome* is length of stay (in days). The Intralipid and ClinOleic groups will initially be compared with unpaired t-test or Mann-Whitney test as appropriate. *Secondary outcomes*: other clinical outcomes (days in ICU, antibiotic-days, infections, mortality) will also be analyzed the same way initially. For secondary outcomes that may change over time, i.e. hs-CRP, pre-albumin and other laboratory results, BMI, arm circumference, hand grip strength, changes will be compared between groups using unpaired t-test or Mann-Whitney test as appropriate. To account for possible covariate effects (eg. age, baseline BMI, Charlson comorbidity index), regression methods such as generalized linear models will be employed. All tests will be based on two-sided alternatives and a test will be considered statistically significant using alpha=0.05. SAS Enterprise Guide 4.1 software (SAS Institute Inc., Cary, NC, USA) will be used.

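### The printed planning figures give about 73% power with 150 per group, not the stated 80%, and the calculator inputs are not reported

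*Combined protocol and SAP*

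**What the plan says.** In Feasibility and Sample Size, Part B, the protocol explains its choice of 150 patients per lipid group: "we based our sample size on a study that evaluated the use of either SO or SO + fish oil (FO) in 206 patients". The length of stay quoted from that study is "Mean (SD) 15(5) versus 17(8) p= 0.041". For detecting a difference of that kind, the protocol states: "we estimate that a sample size of 150 in each group with a power of 0.8 and alpha of 0.05 will be sufficient". It cites an online t-test calculator. It does not report the difference or SD entered, or whether the calculation was one- or two-sided.

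The Statistical analysis section settles sidedness for the trial: "All tests will be based on two-sided alternatives and a test will be considered statistically significant using alpha=0.05". For the primary outcome it leaves the test open: "The Intralipid and ClinOleic groups will initially be compared with unpaired t-test or Mann-Whitney test as appropriate".

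On feasibility, the protocol says "there are about 200 in-patients per year receiving PN" and "it is expected that 90% will agree to participate in the project". It puts the combined total for Parts A and B at 350 and adds: "It is expected to take about one and a half years to recruit this number of patients".

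**The concern.** A reader who puts the printed means and SDs into a standard two-sample calculation does not get 150 per group at 80% power. Length of stay is the primary outcome of the lipid comparison, so this is the trial's main power statement. If it is overstated, the risk of missing a true 2-day difference is higher than the protocol admits, and a non-significant result would be read as stronger evidence of no difference than it is. Because the calculator inputs are not given, the reader cannot tell whether 150 rests on other inputs or is a mistake.

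A smaller point arises in the same section: the stated recruitment period does not follow from the stated patient flow and consent rate.

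**Working it through.** **Inputs.** From Feasibility and Sample Size: means 15 and 17 days, SDs 5 and 8, 150 per group, one-to-one allocation, power 0.8, alpha 0.05. From Statistical analysis: two-sided tests. No dropout allowance is stated, so none is applied.

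**Trying to reproduce the stated figure.**

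- Difference: 17 − 15 = 2 days.
- Pooled SD: √((5² + 8²)/2) = √44.5 = 6.67 days.
- Normal-approximation sample size: n = 2(1.960 + 0.842)² × SD²/difference² = 2 × 7.849 × 44.5/4 = 174.6, so 175 per group. With the noncentral t distribution it is 176.
- Power at 150 per group: the standard error is 6.67 × √(2/150) = 0.770 and the noncentrality is 2/0.770 = 2.60. Power is 73.5% by the noncentral t, 73.5% with Welch degrees of freedom and 73.8% by the normal approximation. A simulation of 40,000 normal-data trials gave 73.8%.
- For 80% power at 150 per group, the difference must be about 2.16 days with SD 6.67, or the SD must be about 6.16 with a 2-day difference.

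**Other readings of the printed inputs (2-day difference).**

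| Reading | Power at 150 per group | n per group for 80% |
|---|---|---|
| Pooled SD 6.67, two-sided | 73.5% | 176 |
| Simple average SD 6.5, two-sided | 75.7% | 167 |
| SD 5, two-sided | 93.2% | 100 |
| SD 8, two-sided | 57.9% | 253 |
| Pooled SD 6.67, one-sided 0.05 | 82.8% | 139 |

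None returns 150 at 80%.

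**Rounding.** The published values are whole days.

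- With a 2-day difference, SDs of 4.5 and 7.5 give 79.7% and SDs of 5.5 and 8.5 give 67.4%.
- With SDs of 5 and 8, a difference of 1.8 days gives 64.4% and 2.2 days gives 81.2%.
- Means that round to 15 and 17 allow any difference from about 1 to about 3 days. Over that full range the power runs from 25% to 97%.

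**The published p-value.** This check assumes a pooled t-test with 103 patients per arm, which the protocol does not state. On 204 degrees of freedom, p = 0.041 corresponds to t = 2.057 and a standardized difference of 2.057 × √(2/103) = 0.287. That gives 69.6% power at 150 per group, and 80% needs about 192. The printed means and SDs under the same assumption give t = 2.152 and p = 0.033, a standardized difference of 2/6.67 = 0.300.

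**Recruitment.**

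- 200 × 0.90 = 180 patients a year, and 350/180 = 1.94 years. The excess over 1.5 years is 0.44 × 12, about 5 months.
- With every patient consenting: 350/200 = 1.75 years.
- Leaving out the first 50 patients of Part A: 300/180 = 1.67 years.
- Reaching 350 in 1.5 years needs 350/1.5 = 233 a year, more than all the PN in-patients the protocol counts.

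The 200 covers all in-patients on PN, while the inclusion criteria under Study design require an expected 5 days or more of PN. On these inputs 180 a year is therefore an upper limit.

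**The case against.** The strongest reply is that the protocol never claims 80% power for exactly 2.0 days. It speaks only of a difference like the one in the cited study, and 2.16 days is just 8% above 2. Rounding adds to this: a difference of 2.1 days with SDs of 4.8 and 7.8, all consistent with the printed integers, gives 79.9%. The integers therefore cannot prove that the original calculation was wrong. This stands, and it limits the finding to what the printed figures deliver. It does not rescue the statement, because the section offers no other number and rounding can lower the power as easily as raise it.

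A one-sided 0.05 calculation needs 139 per group, and an 8–10% dropout allowance would bring that close to 150. That may be where the figure came from. But it contradicts the two-sided rule, and no dropout is stated.

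The p-value check is weak support: it rests on an assumed test and an assumed equal split, and under those assumptions the published figures do not agree with each other. It shows only that the p-value does not point towards 80%.

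Mann-Whitney power depends on a distribution the protocol does not give. It is about 72% for normal data and can go either way with skew, so it plays no part in the main conclusion.

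On recruitment, 300/200 = 1.50 years matches the stated duration. That requires setting aside both the first 50 patients and the 90% consent rate, whereas the sentence refers to the 350 just mentioned.

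**Conclusion.** The point holds. On the printed means and SDs and the trial's own two-sided 0.05 level, 150 per group gives 73.5% t-test power, 6.5 points below the stated 80%. The chance of missing a true 2-day difference is about 27% rather than 20%. The conclusion assumes the printed whole-day values were the inputs, equal groups and no dropout. Unrounded inputs could raise or lower the figure, but the protocol does not show them. What is established is that the stated power cannot be reproduced from what is printed, not which values were entered. The shortfall is modest but affects the primary comparison, so it should be corrected.

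The recruitment period is understated by about 5 months for the full 350 patients, or about 2 months if the first 50 are left out.

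**What to change.** Keep 150 per group and replace the power sentence with a statement such as: with 150 patients per group, an unpaired t-test at two-sided alpha 0.05 has about 73% power for a difference of 2 days (SDs 5 and 8, pooled SD 6.67), or 80% power for a difference of about 2.16 days. If unrounded values from the cited study were entered, print the difference and SD used and the power they give.

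Name the primary test for length of stay. If it is not the t-test, give its power under a labelled distributional assumption, with a range.

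Change the recruitment period to about two years, or state the enrolment rate that supports one and a half years (233 a year).

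These are wording changes and add no patients; the cost is a less favourable stated power and timeline. Raising the sample to 176 per group instead would add 2 × 26 = 52 patients, or 52/180 × 12 = about 3.5 months of recruitment.

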## **Significance**

There are currently no data prospectively collected in Canada that evaluate the indications and outcomes of hospitalized patients with PN in different hospital units. There is a need for prospective interventional studies to compare clinical outcomes between the traditional soybean oil-based lipid emulsion and the olive oil-based lipid emulsion. The results of this project will help establish standards of practice and this will greatly benefit the inpatient population requiring PN.

